APPENDIX 4. TECHNICAL GUIDELINE ON CLINICAL TRIALS OF DRUGS FOR LUPUS NEPHRITIS TREATMENT

Technical Guideline on Clinical Trials of Drugs for Lupus Nephritis Treatment

September 2023

Technical Guideline on Clinical Trials of Drugs for Lupus Nephritis Treatment

I. Introduction

(I) Characteristics of the disease

Lupus nephritis (LN) refers to renal impairment caused by systemic lupus erythematosus (SLE).

With a prevalence of 30.13-70.41/100,000, SLE is the most common systemic autoimmune disease in China. Kidneys are the most frequently affected organs in SLE, and 40%-60% of SLE patients have LN at the beginning of SLE. LN is the most common secondary immune glomerular disease in China and prone to flare (flare rate is 33%-40%). In China, the 10-year renal survival rate in LN is 81%-98%. LN is one of the common causes of end-stage kidney disease (ESKD) and also an important cause of death of SLE patients.

The goal of LN treatment is to protect kidneys, prevent or delay the deterioration of renal function, reduce the incidence rate and mortality of chronic kidney disease (CKD) and renal failure, and reduce drug-related toxicity.

LN treatment usually includes two phases, ie, induction and maintenance. Individualized treatment regimens should be selected based mainly on disease activity, pathological types of kidneys and treatment responses. Few drugs have been approved for LN treatment; additionally, their efficacy is limited, and certain safety problems exist.

(II) Purpose and scope

This guideline aims to provide technical guidance on clinical trials of drugs for LN treatment. This guideline is applicable to the development of chemical drugs and therapeutic biologics. It is used as a recommendatory document. When applying this guideline, please refer also to Good Clinical Practice (GCP), the International Council for Harmonization of Technical Requires for Pharmaceuticals for Human Use (ICH) guidelines, and other relevant guidelines that have been released at home and abroad. This guideline only represents the current views and perceptions of drug regulatory authorities and does not have mandatory legal binding. With the progress of scientific research, this guideline will be constantly improved and updated.

II. General considerations

Overall design of the clinical trial shall depend on the characteristics of drugs, the development goal and objectives of the clinical trial for comprehensive consideration.

(I) Study population

Clinical trials assessing renal outcomes should include patients with active lupus nephritis. Diagnosis of lupus nephritis should be in accordance with the latest generally accepted criteria. SLE disease activity and LN impairment should be documented in detail, including changes in proteinuria, active urinary sediment, and renal function.

Classification should be performed by pathological assessment of renal biopsy to identify pathological types of kidneys. It is recommended to use the 2018ISN/RPS revised criteria and characterize the pathological activity of kidneys and chronicity in LN with activity index (AI) and chronicity index (CI). Renal biopsy should be performed as close as the initiation of study treatment, preferably within 6 months prior to randomization. Combinations of different pathological types of nephropathy may occur, including some special changes in the kidney, eg,

renal tubulointerstitial disease, vascular involvements (eg, lupus thrombotic microangiopathy), and lupus podocytosis, which should all be appropriately assessed.

Considering the impact of baseline levels on efficacy evaluation, stratification may be performed at randomization (eg, histology of lupus nephritis, level of proteinuria, and/or glomerular filtration rate [GFR], etc.). Concomitant medications or other relevant factors that could affect renal outcomes should be documented and taken into consideration in the trial design and analysis of results.

(II) Efficacy measures

Clinical trials of drugs for LN treatment are intended to assess drug efficacy and safety, including clinically significant improvement, eg, improving the estimated or measured glomerular filtration rate (eGFR or mGFR), reducing renal injury, slowing CKD progression, preventing recurrence etc. However, in view of the complexity of LN, measurement of disease activity by a single index alone is considered insufficient to fully reflect the therapeutic effect in individual patients. It is recommended to assess the disease activity through validated composite indices. Currently recommended efficacy indices include complete renal response rate, partial renal response rate, global activity of SLE (SLEDAI or BILAG scale), active urinary sediment, proteinuria, change in serum creatinine and GFR values etc.

Complete renal response should represent clinically significant improvement in renal function. For example, complete renal response can be regarded if both of the following conditions are met: ① urine protein quantification <0.5 g/24 h or urine protein/creatinine ratio (UPCR) <0.5 g/g; ② eGFR reduction $\leq 10\% \sim 15\%$ of baseline or eGFR ≥ 90 mL/min/1.73 m².

Partial renal response represents clinical improvement in renal function, which can maintain GFR within the predefined limit relative to baseline but does not fulfill the criteria for complete response. For example, partial renal response can be regarded if both of the following conditions are met: ① urine protein quantification reduction $\geq 50\%$ of baseline and <3.5 g/24 h, or UPCR reduction $\geq 50\%$ of baseline and <3.0 g/g; ② eGFR reduction $\leq 10\%\sim15\%$ of baseline or eGFR ≥ 90 mL/min/1.73 m².

Attention should be paid to patient reported outcomes, and validated scales are recommended to assess physical, psychological, and social effects, such as 36-Item Short Form Health Survey (SF-36), Fatigue Severity Scale (FSS), FACIT fatigue scale or Brief Fatigue Inventory (BFI) etc.

(III) Other considerations

In case of novel designs such as adaptive design or any content not specified herein, prior communication with the drug regulatory authority is recommended.

In multi-regional clinical trials, consideration should be given to the potential impact of differences in disease characteristics, drug pharmacokinetics/pharmacodynamics (PK/PD) profiles and clinical practices on ethnic sensitivity evaluation. Entry into global development in the early phase is recommended to obtain PK, PD or PK/PD, efficacy and safety data in the Chinese patient population.

III. Clinical pharmacology studies

Clinical pharmacology should be investigated throughout drug clinical trials. Depending on drug characteristics, clinical pharmacology trial protocols should be designed for suitable populations

with reference to relevant guidelines, with consideration given to specific populations (eg, hepatic/renal insufficiency, the elderly, children, etc.).

The dose-exposure-effect relationship of drugs should be fully characterized, and the safety of drugs should be understood to provide basis for selection of appropriate dose regimens and dose modifications in subsequent clinical trials. Where biologics are involved, consideration should be given to the impact of drug immunogenicity on safety and efficacy.

IV. Exploratory clinical trials

Multi-center, randomized, double-blind and placebo parallel controlled design where the placebo is given in add-on to standard of care is recommended.

Based on previous PK/PD study results, multiple dose groups may be set to explore dose-response relationships of drugs. For drugs being investigated in 2 or more autoimmune diseases extrapolation of dose-finding across indications could be acceptable subject to adequate justification.

Duration of the study depends on the lupus patient profile (eg, severity of renal impairment), effect of the drug, study objectives and the corresponding endpoints.

For efficacy measures, the section regarding confirmatory clinical trials may be referred to.

Necessary drug-drug interaction studies should be conducted as early as possible to evaluate the effects of possible concomitant drugs used in clinical practices (eg, glucocorticoids, immunosuppressants) on efficacy and safety and to support the proposed concomitant medication design in confirmatory studies.

V. Confirmatory clinical trials

(I) Overall design

Multi-center, randomized, double-blind and parallel controlled design is recommended. The duration of confirmatory clinical trials is long, and studies should be conducted on the basis of standard of care. Superiority trial design against an active comparator or placebo is preferred. Non-inferiority studies could only be accepted provided that the selected comparator could be justified on the basis of a well-established efficacy, and an appropriately justified non-inferiority margin could be predefined. Such comparative studies must have assay sensitivity. For add-on trials, superiority design is recommended.

(II) Selection of controls

Placebo-controlled trials aim to evaluate the absolute efficacy of test drugs. Active-controlled studies aim to demonstrate the test drugs are superior or non-inferior to the control drugs. Subject populations for different clinical trials may differ in disease severity, disease progression risk and endpoints for efficacy assessment. Appropriate control drugs should be selected depending on the goal of drug development.

(III) Subjects

Specific inclusion/exclusion criteria should be developed depending on proposed indications and development goals. Inclusion of clinically active and biopsy-confirmed LN patients is recommended. The disease severity (including clinical indices and pathological changes) and prior medications should be evaluated.

(IV) Duration of therapy

LN is a chronic disease that require long-term drug therapy. In clinical trials on LN, the efficacy and safety of drugs in inducing response and maintaining therapeutic effects should be comprehensively evaluated. The minimum optimal duration should be 3 to 6 months for induction of partial response. At least 1 year might be needed for induction of complete renal response. For drugs for both induction and maintenance, an additional 1 year is required to observe maintenance of treatment effect after achieving a response. For clinical trials studying only the maintenance of treatment effects, the duration of treatment should be at least 1 year. Tapering the immunosuppressants after induction and/or maintenance period should be predefined and assessed thoroughly during the trial (if applicable).

(V) Efficacy measures

Clinical efficacy measures should be set based on the mechanisms of action of new drugs, therapeutic goals and study objectives.

- 1. Primary efficacy measures
- 1.1 Induction of complete renal response: assessment of the treatment effect of induction therapy, ie, the proportion of subjects achieving the criteria for complete renal response.

Partial renal response could only be accepted as primary endpoint if prospectively defined and relevance is well justified. For such situations, communication with the regulatory authority is recommended. If partial renal response is defined as the primary endpoint, complete renal response should be defined as a key secondary endpoint.

- 1.2 Maintenance of complete renal response and/or prevention of LN flares: assessment of the treatment effect of long-term maintenance therapy, ie, treatment effect in maintaining complete renal response and preventing LN flares (in terms of both incidence and severity).
- 1.3 Prevention of long-term damage and slowing CKD progression. The purpose is to slow GFR reduction, delay the occurrence of ESKD and primary complications (such as cardiovascular diseases). For efficacy measures, it is recommended relevant guidelines be consulted.

2. Secondary efficacy measures

Proportion of subjects achieving the criteria for partial renal response.

The changes of laboratory indices showing either activity of the renal disease or chronic damage, such as active urinary sediment, proteinuria and renal function, including serum creatinine and GFR values.

Assessment of whether reduction of doses of glucocorticoids and/or immunosuppressants is favored.

Clinical indices of SLE: presence of SLE manifestations, assessment of overall SLE activity.

Where possible, repeated renal biopsies after treatment for 6 months are recommended to assess changes in renal pathology (eg, activity and chronicity indices).

Long term renal outcomes: development of ESKD with requirement of chronic renal replacement therapy and/or transplantation.

(VI) Concomitant treatment

During drug clinical trials, changes in dosages and administration of concomitant drugs can affect the treatment effect of the study treatment. Therefore, concomitant treatment should be standardized and kept stable and balanced among groups as far as possible. If modifications of concomitant drugs (eg, ACEI or ARB) may be made during the clinical trial, corresponding regimens should be predefined in the clinical trial protocol.

(VII) Rescue therapy

With regard to the potential risk of disease exacerbation, the rescue therapy criteria and rescue therapy drugs should be predefined in the protocol to ensure the safety of subjects in clinical trials. The estimand should be defined for rescue therapy, which is regarded as an intercurrent event. For specific requirements, refer to E9R1.

VI. Safety evaluation

In principle, the common standards for safety evaluation should be followed.

(I) Specific adverse events to be monitored

Considering that the risks of infection, cardiovascular events and malignancies are greater in SLE patients, such events should be specifically monitored. Given that the kidney is an important target organ for SLE and patients with SLE often have concomitant renal impairment, potential impact of the new agent on renal function or, in turn, any influence of renal impairment on drug elimination should be adequately monitored. Adverse events related to common organs/systems involved in SLE should also be closely monitored. Long term follow-up data must be available.

(II) Long-term safety

LN is a chronic disease, and most drugs will need to be administered on a long-term basis. Therefore, sufficient exposures and exposure duration are required for safety observation. Reference to ICH E1 is recommended. Setting of an Independent Data Monitoring Committee in long-term trials is recommended. In clinical trials on LN, special consideration should be given to the following safety evaluation items:

- 1. Drugs for LN treatment typically exert influence on the immune system. Special attention should be paid to the possibility of risks of developing serious infections and malignancies.
- 2. For biologics, consideration should be given to immunogenicity and whether anti-drug antibodies developed due to immunogenicity affect the long-term efficacy and safety of the drug. Concomitant use of immunosuppressants may reduce the ability to detect immunogenicity, so special attention should be paid to concomitant medications in safety evaluation.
- 3. For further identification of rare adverse events associated with new drugs, intensive safety evaluation during randomized trials might contribute but long-term follow-up in a large population will be needed.

VII. References

[1] EMA, Guideline on clinical investigation of medicinal products for the treatment of systemic lupus erythematosus and lupus nephritis. 26 February 2015.

[figure not shown]
- [2] Chinese Guidelines for the Diagnosis and Treatment of Lupus Nephritis Drafting Group. Chinese guidelines for the diagnosis and treatment of lupus nephritis [J]. Med J China, 2019, 99 (44): 3411-3455.
- [3] Chinese Society of Rheumatology, Chinese Medical Association. Diagnosis and Treatment Standard of Lupus Nephritis. Chin J Intern Med, 2021, 60(9): 784-790.
- [4] NMPA. Guideline on General Considerations in Drug Clinical Trials. 18 January 2017.
- [5] Ingeborg M. B, Suzanne W, Charles E. A, et al. Revision of the ISN/RPS classification for lupus nephritis: clarification of definitions, and modified NIH activity and chronicity indices. Kidney Int. 2018; 93 (4): 789-796.
- [6] Kidney Disease: Improving Global Outcomes (KDIGO) Glomerular Diseases Work Group. KDIGO 2021 Clinical Practice Guideline for the Management of Glomerular Diseases. Kidney Int.2021; 100 (4S): S1-S276.

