#### PATIENT SELECTION:

**Targeted Number of Patients:** Approximately 249 patients will be enrolled with Class III/IV +/-V LN. Up to 30 additional patients with pure Class V LN may be enrolled, for a total of up to approximately 279 patients.

**Planned Number of Sites:** Approximately 250 sites are planned to participate in this study. Inclusion Criteria:

- 1. Is able to provide written informed consent before any study-related procedures are performed.
- 2. Is aged  $\geq$ 18 years at the time of signing the informed consent.
- 3. Has a body mass index of  $\geq 18 \text{ kg/m}^2$ .
- 4. Has a diagnosis of systemic lupus erythematosus (SLE) according to the 2019 American College of Rheumatology/European Alliance of Associations for Rheumatology (ACR/EULAR) criteria (Aringer et al., 2019).
- 5. Has an unequivocally positive antinuclear antibody (ANA) test result, defined as an ANA titer ≥1:80 (based on Hep-2 immunofluorescence assay or equivalence by enzyme immunoassay assay) and/or a positive anti-double stranded DNA (anti-dsDNA) (≥30 IU/mL based on the enzyme-linked immunosorbent assay) serum antibody test at the Screening visit.
- 6. Has a diagnosis of LN according to 2003 or 2018 International Society of Nephrology/Renal Pathology Society (ISN/RPS) criteria of either:

- a. Class III or IV LN as evidenced by renal biopsy performed within 12 months prior to or during Screening. Patients may co-exhibit Class V disease in addition to either Class III or IV disease. For biopsies >6 months prior to the Screening visit, at least 1 of the following must also be present at Screening: low C3, low C4, or anti-dsDNA elevated above the normal range.
- b. Pure Class V LN as evidenced by renal biopsy performed within 12 months prior to or during Screening. In addition, a stable dose of a renin-angiotensin-aldosterone system inhibitor (RAASi) anti-hypertensive medication must be used for at least 1 month prior to screening and a systolic blood pressure of ≤130 mm Hg must be present at Screening.
- 7. Has confirmed proteinuria defined for
  - a. Class III/IV +/-V LN with UPCR of ≥1.0 assessed in two 24-hour urine samples during the Screening period at least 7 days apart (see Section 7.2.2.2).
  - b. Pure Class V LN with UPCR of ≥2.0 assessed in two 24-hour urine samples during the Screening period at least 7 days apart (see Section 7.2.2.2).

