8.5.3. Analysis of Binary Exploratory Endpoints

Binary exploratory endpoints include:

- Proportion of patients achieving PRR with successful taper of prednisone or equivalent to ≤5 mg by Week 17
- Proportion of patients achieving PRR with no use of prednisone or equivalent during the 8 weeks prior to the renal response assessment

- Proportion of patients who meet CRR by the China Center for Drug Evaluation (CDE) of NMPA Technical Requirements (Appendix 4), which is achieved if both of the following conditions are met:
 - urine protein quantification <0.5 g/24 h or urine protein/creatinine ratio (UPCR)
 <0.5 g/g;
 - eGFR reduction ≤10% of baseline or eGFR ≥90 mL/min/1.73 m².
- Proportion of patients who meet PRR by the CDE Technical Requirements definition (Appendix 4), which is achieved when both of the following conditions are met:
 - partial renal response can be regarded if urine protein quantification reduction ≥ 50% of baseline and <3.5 g/24 h, or UPCR reduction ≥ 50% of baseline and <3.0 g/g;

and

- eGFR reduction ≤ 10% of baseline or eGFR ≥90 mL/min/1.73 m².
- Proportion of patients who achieve urine protein quantification <0.5 g/24 h or urine protein/creatinine ratio (UPCR) <0.5 g/g and eGFR reduction ≤20% of baseline or eGFR >60 mL/min/1.73 m².
- Proportion of patients who achieve urine protein quantification <0.5 g/24 h or urine protein/creatinine ratio (UPCR) <0.5 g/g and eGFR reduction ≤15% of baseline or eGFR ≥60 mL/min/1.73 m².
- Proportion of patients who develop doubling of Baseline serum creatinine, kidney failure (receiving dialysis or kidney transplantation), or death
- Proportion of patients with Baseline SLEDAI-2K, excluding renal components, ≥6 with at least a 4-point improvement
- Proportion of patients with relapse or proteinuric flare
- Proportion of patients with SLE Flare Index of severe, moderate, or mild

The binary exploratory endpoints will be analyzed using similar CMH methods as the main analysis of the primary estimand.

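### The CDE partial-response endpoint in SAP 8.5.3 omits the guideline's exclusion of complete responders, so the rate it reports is essentially that of at least a partial response

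*SAP*

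**What the plan says.** SAP 8.5.3 (Analysis of Binary Exploratory Endpoints) has two endpoints taken from the CDE guideline.

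- **CDE CRR.** Proteinuria: "urine protein quantification <0.5 g/24 h or urine protein/creatinine ratio (UPCR") below 0.5 g/g. Renal function: "eGFR reduction ≤10% of baseline or eGFR ≥90 mL/min/1.73 m²".
- **CDE PRR.** The endpoint is "PRR by the CDE Technical Requirements definition (Appendix 4), which is achieved when both of the following conditions are met". Proteinuria: either "urine protein quantification reduction ≥ 50% of baseline and <3.5 g/24 h" or "UPCR reduction ≥ 50% of baseline and <3.0 g/g". The renal-function condition has the same limits as for CRR.

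Neither PRR condition removes patients who meet CRR. The CDE endpoints do not appear in SAP Table 1 or among the added endpoints listed in SAP Section 13, so no other text supplies the exclusion.

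Appendix 4, under Efficacy measures, first says what partial response is: an improvement "which can maintain GFR within the predefined limit relative to baseline but does not fulfill the criteria for complete response". It then gives numeric conditions, introduced as an example. These are the conditions the SAP uses, with the guideline's 10% to 15% eGFR allowance fixed at 10%.

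Protocol inclusion criterion 7a requires "Class III/IV +/-V LN with UPCR of ≥1.0 assessed in two 24-hour urine samples".

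**The concern.** The SAP names Appendix 4 as the source of its definition but drops one element of it. CDE CRR and CDE PRR are then each compared between arms by CMH and reported as separate endpoints. A reader who knows the guideline would take the PRR line as the patients who improved without reaching complete response. If the line also contains the complete responders, a difference in CRR reappears under the PRR label and can be mistaken for a separate effect on partial response.

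**Working it through.** The documents state no rate, power or sample size for the CDE endpoints, so there is no plan figure to reproduce. The check has two parts: whether CDE CRR is nested in the SAP's CDE PRR, and what that does to a reported difference.

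**Nesting, UPCR route.** Let B be baseline UPCR and U the later value. If B ≥ 1.0 and U < 0.5, the reduction is 1 − U/B > 1 − 0.5/1.0 = 50%. U is also below 3.0, and the eGFR condition is shared. Every such complete responder meets the PRR rule.

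**Nesting, 24-hour protein route.** If baseline protein is at least 1.0 g/24 h and the later value is below 0.5 g/24 h, the same algebra gives a reduction above 50%, and the value is below 3.5 g/24 h. The rule is met again.

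**Exceptions.** There are two kinds.

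- *Baseline protein below 1.0 g/24 h, with complete response reached on protein only.* Suppose protein goes from 0.80 to 0.45 g/24 h and UPCR from 1.0 to 0.56, with eGFR preserved. The protein reduction is 1 − 0.45/0.80 = 44%, and UPCR falls by the same share. CRR is met and PRR is not.
- *Baseline average UPCR below 1.0.* Protocol 7.2.2.2 allows a third screening collection when one fails. Protocol 10.6 averages the non-missing screening results and does not let repeats replace originals. Values of 1.0, 0.5 and 1.0 average 0.83. A later UPCR of 0.45 is a reduction of 1 − 0.45/0.83 = 46%. If creatinine excretion is unchanged, the protein route fails as well.

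A grid over baseline UPCR 1.0 to 8.0, later UPCR 0.01 to 4 and creatinine excretion 0.4 to 2.0 g/day agrees with the algebra. It gave 0 exceptions in 284,954 points on the UPCR route and 990 in 64,090 on the protein-only route, all with baseline protein below 1.0 g/24 h. These counts show where exceptions lie, not how often patients fall there.

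**Effect on a reported difference.** CRR is set at the design rates of 40% versus 20% with 83 per arm (SAP 4.2). Those rates belong to the trial's own CRR and are borrowed here for scale. The partial-only rate is in neither document and is assumed. The rare exceptions are ignored. The test is an unstratified pooled z, with p̄ the mean of the two SAP-rule rates: z = difference / √(2·p̄(1 − p̄)/83).

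| Assumed partial-only (active / placebo) | SAP rule | z, nominal p | Partial-only difference |
|---|---|---|---|
| 20% / 20% | 60% vs 40% | 0.20/√(2·0.50·0.50/83) = 2.58, p = 0.010 | 0 |
| 30% / 30% | 70% vs 50% | 0.20/√(2·0.60·0.40/83) = 2.63, p = 0.009 | 0 |
| 15% / 30% | 55% vs 50% | not computed | −15 points |

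The last row is a drug that moves patients from partial to complete response. The inclusive rate rises by 5 points while the partial-only rate falls.

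For scale, Protocol 1.1.2 cites about 50% responding and about 25% in complete response on standard therapy. Under those different definitions, 25/50, or half, of an inclusive rate would be complete responders.

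**The case against.** The strongest defence is that the SAP follows the guideline's operational criteria. The numeric example in Appendix 4 does not repeat the exclusion, the guideline calls itself recommendatory, and the SAP prints its rule in full, so anyone can see that complete responders qualify. The trial's own PRR (Protocol 2.2.1, SAP 3.2.1.2) is inclusive too, so an exclusive CDE PRR would give one term two meanings in the same report. The last row of the table also shows that an exclusive endpoint can make a beneficial drug look harmful.

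Most of this stands. An inclusive rate is a legitimate measure and the better one to test. What does not stand is the attribution: the SAP says it applies the Appendix 4 definition, and the sentence there that says what partial response is excludes complete response. The trial's own PRR makes no claim to follow the CDE.

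A reader might go further and infer that the endpoint is exactly CRR plus PRR, that the SAP breaches a binding requirement, or that it adds the two rates or treats them as independent evidence. The documents support none of these. The nesting has the exceptions shown, the guideline disclaims binding force, and no SAP text combines the two rates.

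**Conclusion.** The point holds as one of labelling and interpretation, and it is minor. The SAP's CDE PRR is essentially the proportion with at least a partial response, and a difference in it can arise wholly from CRR. The near-complete overlap follows from the entry criterion and the shared eGFR condition. It assumes that non-responder handling is applied to both endpoints alike, as the common reference to the primary-estimand methods suggests. The size of any misreading depends on the unknown partial-only rate: the 20-point differences above rest on assumed equal rates of 20% to 30%, and the p-values are illustrative.

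It would be wrong to infer that the trial's efficacy conclusions are at risk. The endpoint is exploratory and outside type I error control (SAP 8.1). The primary and key secondary analyses, power and interim rules do not use it.

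**What to change.** In SAP 8.5.3:

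1. Label the present rule *CDE complete or partial renal response* and keep its planned CMH comparison.
2. Add a descriptive three-level count by arm: CDE CRR; CDE PRR, meaning the partial conditions are met and the CRR conditions are not; no response. Assign CRR first.
3. Attach no separate test to the PRR-only level, because its difference can reverse when the drug moves patients from partial to complete response.
4. Footnote that the few patients who meet CRR but not the 50% reduction appear under CRR in the count and are not in the inclusive rate, so the figures may not add exactly.

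The cost is a wording change, one derived variable and one short table. No new data are needed.
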